4. VERSION DATE 7/26/16

5. SPECIFIC AIMS

Aim 1: Assess the relationship of treatment with the combination of dronabinol and clonidine or placebo on cannabis use patterns in cannabis-dependent subjects with an Axis 1 psychiatric disorder.

Aim 2: Assess the relationship of treatment with the combination of dronabinol and clonidine or placebo on cannabis withdrawal symptoms in cannabis-dependent subjects with an Axis 1 psychiatric disorder.

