- 8.2.1.d. Availability and Flow of Subjects into Treatment. We plan to screen 50 subjects in the course of 20 months to achieve our desired sample size.
- 8.2.1.e. Study Visits. Following eligibility for the study (as determined by the baseline-1 visit), subjects will come to the laboratory for a baseline-2 visit to complete research assessments, provide a urine sample, and begin daily diaries and Actiwatch (see Section 8.5.2.a.) Subjects will then come to the clinic twice a week during the study medication treatment phase. One visit will include a medical visit (dispensing of pills and Medical Management; see Sections 8.3.1.b, 8.3.2) and research assessments, including a urine screen (see Section 8.5.2.a and Table 8.2). The other visit will consist only of a urine screen (see Section 8.5.2.a). After the 10-week treatment period, participants will have a follow-up assessment visit at 14 weeks. Subjects will also come in once weekly during weeks 11, 12, and 13 following the 10-week treatment period to provide a urine sample, and hand in daily diaries/actiwatch.

Subjects will be randomized to receive either dronabinol and clonidine or placebo. [name] or the research assistants will present 7 day prescriptions to the McLean pharmacy and the subject will receive blister packs containing 1 week of medication or placebo, separated into daily doses. Subjects will be asked to return unused pills at each weekly medical visit; study staff will then perform a pill count for the study record. All groups will receive capsules following the same schedule: 2 capsules three times daily for 10 weeks. Each capsule will contain either dronabinol, clonidine, or placebo. Subjects in the dronabinol-clonidine group will take 5 mg of dronabinol three times daily for 10 weeks (between 7:00-9:00 AM, 3:00-5:00 PM and 9:00-11:00 PM). Subjects in this group will also take clonidine 0.1 mg po bid (between 7:00-9:00 AM and 9:00-11:00 PM) for 8 weeks, followed by a taper to clonidine 0.1 mg po qhs for the last 2 weeks of

Partners Human Subjects Research Application Form

Version Date: July 26, 2016

the protocol. Subjects will be assessed for side effects prior to each dosing increase and the study physician will decide if increasing the dose as scheduled is appropriate. See Table 1 for a schedule of study visits.

Table 1	Cabadula	of Magazinas
i abie i	Scheaule	of Measures

Table 1 Schedule of Measures					
Measure	Baseline 1 and 2	•	_		Week 14

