		Week	1	Weeks 5,10	
Diagnostic Assessment					
Structured Clinical Interview	X B1				
for DSM-IV ^a	ABI				
Drug and Alcohol Assessment					
2. Quantitative Urine Toxicological	XB1,B2	X^{b}	X	X	X
Analysis ^b	•				
3. Addiction Severity Index	XB2		X	X	X
4. Drug and Alcohol Use Questionnaire	XB1				
5. Weekly Drug and Alcohol Use Inventory	XB1,B2	X	X	X	X
6. Marijuana Goals Questionnaire	XB1				
7. Marijuana Craving Questionnaire	XB1,B2	X	X	X	X
8. Marijuana Withdrawal Checklist	XB1,B2	X	X	X	X
Mood and Impulsivity Assessment					
9. Quick Inventory of Depressive	TID1 DA			***	***
Symptomatology	XB1,B2			X	X
10. Barratt Impulsiveness Scale	XB1,B2			X	X
11. Beck Anxiety Inventory	XB1,B2			X	X
Medical & Safety Assessment	VD1				37
12. Physical examination 13. ECG	XB1 XB1				X
	XB1,B2	X	X	X	X X
14. Urine pregnancy test	AD1,D2	Λ	Λ	Λ	Λ
15. Vital Signs ^c	XB1,B2	X	X	X	X
16. Positive and Negative Syndrome Scale	XB1,B2				
17. Behavioral Activity Rating Scale	XB1		X		
18. Laboratory tests ^d	XB1			X	X
19. Adverse Events & Side Effects	XB1,B2	X	X	X	X
20. Columbia Suicide Severity	XB1	X	X	X	X
21. Marijuana Perceptions of Risk and	XB1			X	X
Experiences Questionnaire (MPRE)					
Rating Scale					

^aFull SCID at baseline

8.2.1.f. Clinical Emergencies. If a subject is intoxicated, the subject will be evaluated medically, sent home in a taxi when safe, and the appointment re-scheduled. If a subject experiences a problem that requires clinical intervention during the course of the study (e.g., mania, suicidal ideation, or dangerous intoxication), we will evaluate the situation medically, make an appropriate recommendation, and help the subject to implement this plan. This could involve hospitalization at McLean, referral to the hospital's outpatient program, or other medical or psychiatric treatment, as clinically appropriate.

Partners Human Subjects Research Application Form

^bTwice a week during treatment

^cVital Signs include pulse and blood pressure (sitting and standing)

^dTests include urinalysis, liver function tests, electrolytes, complete blood count, & blood chemistries B1= Baseline 1 (screening visit)

B2=Baseline 2 (baseline 2 visit post screen for subjects who qualify for participation before treatment begins)

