8.2.1.g. Subject Payments. Volunteers will receive a \$50 honorarium for attending the initial assessment interview, \$25 for baseline-2 visit, and \$50 for follow-up visits at 5, 10, and 14 weeks. They may earn \$25 for each urine sample given on a non-MM day in the first 5 weeks of the treatment and \$30 for each urine sample given on a non-MM day during the last 5 weeks of treatment. They will be compensated \$50 for the Week 1 monitoring visit and \$30 for each of three actiwatch diary UA visits at wks 11,12, and 13. They may also receive a bonus of up to \$100 for successful completion of all diaries. They may earn a total of \$740 for their participation in the study. Medication will be free.

A payment request will be submitted for each part of the study they finish. The research assistants will arrange for payment to be sent via mail to the subjects.

8.3. Treatment. ([name] has been granted IND 108676 by the FDA to use this medication combination in this protocol.)

Dronabinol (Marinol[®], Solvay Pharmaceuticals, Marietta, GA) is an orally-active cannabinoid agonist that is approved by the FDA for the treatment of anorexia associated with weight loss in patients with AIDS and nausea and vomiting associated with cancer chemotherapy (Marinol[®] product information). Dronabinol will be titrated to 5 mg three times daily in the dronabinol-clonidine group. Doses of up to 90 mg of dronabinol daily have been well-tolerated in studies of its effects upon cannabis-dependent individuals (Levin and Kleber 2008, Haney et al. 2008, Haney et al. 2004, Budney et al. 2007).

Clonidine (Catapres[®], Boehringer Ingelheim Pharmaceuticals, Ridgefield, CT) is α_2 -adrenergic agonist that is approved by the FDA for the treatment of hypertension (Catapres[®] product information). Clonidine will be administered at 0.1 mg twice daily in the dronabinol-clonidine group prior to a 2-week taper to clonidine 0.1 mg po qhs.

Placebo will be vegetable capsules (Gallipot, Inc., St. Paul, MN) double encapsulated into 00 capsules.

Physicians are ACLS-trained and have access to a "crash cart" located in the laboratory. All study personnel are basic life support-trained and have practiced assisting a physician in the event of an emergency.

8.3.1.c. Dose Adjustment.

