baseline and weekly during treatment and at the 14-week follow-up visit (Heishman et al. 2009). A short form of the Marijuana Withdrawal Checklist will be used to assess withdrawal symptoms at baseline and weekly during treatment and at the 14-week follow-up visit (Budney et al. 1999). If there is a discrepancy among results obtained by these methods of substance use assessment, we will meet with the subject and have a conversation about their substance use. After the conversation, we will use our clinical judgment to determine the level of use that we believe is most accurate for that subject. A 6-page questionnaire that we created titled Marijuana Perceptions of Risk and Experiences (MPRE), will be distributed at baseline, and once during weeks 5, 10 and 14 to assess each participant's perceptions of cannabis risk/harm and his or her motivations to quit/continue using cannabis throughout the course of treatment.

- 8.5.3. Mood and Impulsivity Assessments. We will monitor subjects' mood and impulsivity throughout the study using 3 assessments. The Beck Anxiety Inventory (BAI) is a 21-item self-report measure that can be used to assess the severity of anxiety. The Quick Inventory of Depressive Symptomatology (QIDS-SR) is a short self-report questionnaire for depressive symptoms used successfully in the STAR*D project. The Barratt Impulsiveness Scale (BIS-11) is a commonly used tool to measure impulsivity in various neuropsychological disorders as well as in substance abuse. Three dimensions can be assessed using this scale, which include Cognitive Impulsivity, Motor Impulsivity, and Non-planning Impulsivity.
- 8.6. Medication Adherence Assessment. The proposed studies involve chronic administration of medication given under double-blind conditions. Three methods of medication adherence will be used as multiple methods are preferred (Weiss 2004): 1) pill counts will be made; 2) subjects will record when they take their capsules on the ActiWatch-Score device; 3) urinary riboflavin levels (a 25 mg dose will be given with each dose of medication) will be measured using a UV spectrophotometer. If there is a discrepancy among results obtained by these methods, we will meet with the subject and have a conversation about their medication adherence. After the conversation, we will use our clinical judgment to determine the level of adherence that we believe is most accurate for that subject.

8.8. Data Management

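### No withdrawal or craving scale is given at the week 11, 12 and 13 visits, so a short return of symptoms after scheduled dronabinol ends would not be recorded on the Aim 2 scale

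*Combined protocol and SAP*

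**What the plan says.** - **Aim.** Section 5, Aim 2: "Assess the relationship of treatment with the combination of dronabinol and clonidine or placebo on cannabis withdrawal symptoms". No time window is stated.
- **Scale and timing.** Section 8.5.2.c: the short-form Marijuana Withdrawal Checklist "will be used to assess withdrawal symptoms at baseline and weekly during treatment and at the 14-week follow-up visit". The 12-item Marijuana Craving Questionnaire has the same timing. Table 1 is consistent with this as far as its damaged column headings can be read, but the text of 8.5.2.c settles the schedule without it.
- **Drug exposure.** Section 8.2.1.e: "Subjects in the dronabinol-clonidine group will take 5 mg of dronabinol three times daily for 10 weeks". No dronabinol taper is described. Clonidine is reduced for the last 2 weeks, so both drugs end at week 10.
- **Visits after treatment.** Section 8.2.1.e: "Subjects will also come in once weekly during weeks 11, 12, and 13 following the 10-week treatment period to provide a urine sample", together with diary and ActiWatch hand-in. Section 8.5.2.b lists the same content, and Section 8.2.1.g pays "for each of three actiwatch diary UA visits at wks 11,12, and 13".
- **Other instruments.** In Table 1 the depression, anxiety and impulsivity scales are given at baseline and at weeks 5, 10 and 14, so not in weeks 11 to 13.
- **Analysis.** Section 8.9 has no analysis specific to withdrawal. Section 8.1 says only that mixed models ANOVA will be applied to the data.

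**The concern.** The active treatment contains a cannabinoid agonist, and one cited study, by its title, reports that oral THC suppresses cannabis withdrawal. Lower on-treatment scores in the active arm would therefore be expected in two cases: the combination helps people through withdrawal, or it holds symptoms down until the agonist stops. The weeks just after the last dose are the most informative for telling these apart, and the scale is not given then.

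Section 6 presents withdrawal as an obstacle to stopping cannabis, and Section 8.1 uses follow-up to judge how durable the effects on drug use are. Urine and diaries could show a return to use in weeks 11 to 13, but no checklist score would show whether withdrawal came with it.

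**Working it through.** The plan states no figure to reproduce here, so the check rebuilds the visit calendar.

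**1. Do the week 11 to 13 visits exist?** The payment items in Section 8.2.1.g are $50 for the initial interview, $25 for baseline-2, $50 for each of 3 follow-up visits, $25 for each of 5 urine samples, $30 for each of 5 urine samples, $50 for week 1 monitoring, $30 for each of 3 visits in weeks 11 to 13, and a $100 diary bonus:

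50 + 25 + 3×50 + 5×25 + 5×30 + 50 + 3×30 + 100 = 740

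This equals the stated total of $740, so three paid visits are planned in those weeks.

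**2. Time since the last scheduled dose.** Week 10 ends on day 70. A visit in week w falls between 7(w − 1) + 1 − 70 and 7w − 70 days later.

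| Week | Days after last dose | Checklist as planned | Checklist with the change |
|---|---|---|---|
| 11 | 1–7 | no | yes |
| 12 | 8–14 | no | yes |
| 13 | 15–21 | no | yes |
| 14 | 22–28 | yes | yes |

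Post-treatment checklists rise from 1 to 4, and the first falls 1–7 days after the last dose instead of 22–28.

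**3. What would be recorded?** The documents give no duration for symptoms after stopping, so duration is an assumption shown as a range. Symptoms are taken to start at the last dose, with each visit at the end of its week.

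| Assumed duration | Checklists in the window, as planned | With the change |
|---|---|---|
| 1 week | 0 | 1 |
| 2 weeks | 0 | 2 |
| 3 weeks | 0 | 3 |
| 4 weeks or more | 1 | 4 |

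Assuming a 7-day recall period for the checklist gives the same counts. Between 3 and 4 weeks, capture depends on the day of the week-14 visit.

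**4. How much could the added scores show?** Half of 18 is 9 per arm; with 20% dropout, 9 × 0.8 = 7.2. For a between-arm difference of 1 SD (an assumption; the documents give no effect size or SD) at one visit, two-sided 5%, normal approximation, power = Φ(√(n/2) − 1.96):

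- n = 9: Φ(2.121 − 1.96) = 0.56
- n = 7: Φ(1.871 − 1.96) = 0.46

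The 95% half-width with 9 per arm is 1.96 × √(2/9) = 0.92 SD. Averaging weeks 11 to 13 multiplies the standard error by √((1 + 2ρ)/3), which is 0.82 at ρ = 0.5 and 0.97 at ρ = 0.9, where ρ is an assumed within-subject correlation. The added scores support estimation, not a test.

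**The case against.** The strongest case against is that Aim 2 is already answerable. It asks how treatment relates to withdrawal, and the weekly on-treatment checklists address that. Section 8.1 ties durability to drug use and psychosocial outcomes and does not name withdrawal. This stands: separating relief from postponement is a reasonable further question, not a stated objective.

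Several stronger readings are tempting and go too far:

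- **That withdrawal is wholly unmeasured in weeks 11 to 13.** Section 8.5.2.b says the ActiWatch can monitor craving and sleep, and the diary asks about eating. These are indirect data. Sections 8.5.2.b and 8.9 present both as measures of cannabis use, and neither is defined as a withdrawal outcome.
- **That every active-arm score is taken on THC or four weeks after it.** Baseline scores precede drug. Section 8.3.1.c keeps subjects who stop for intolerance in research visits, and Section 8.9 promises continued assessment of dropouts, so early stoppers may give checklists soon after stopping. They would be few and self-selected, and for some stops Section 8.3.1.b provides follow-up visits only.
- **That a treatment which only postpones withdrawal would be declared a success.** The plan has no success rule for Aim 2, and Section 8.9 calls the outcomes exploratory.
- **That withdrawal will return.** The cited title concerns suppression, not rebound.

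Two practical objections also stand. Resumed cannabis use could itself lower scores in weeks 11 to 13, so low scores would be ambiguous without data on use. And Section 8.9 specifies no analysis even for the withdrawal scores already planned, which is a more basic gap.

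**Conclusion.** The gap is real and follows from the text alone: no withdrawal scale and no Craving Questionnaire at three visits already held, in the first three weeks after scheduled dronabinol ends. The on-treatment effect remains estimable. What is weakened, for subjects who complete treatment, is the ability to see whether symptoms return after stopping. That rests on one checklist 22–28 days later plus indirect data, and similar scores in both arms at week 14 would fit either explanation.

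The size depends on an assumed duration: up to about 3 weeks, a return is not recorded on the scale; at 4 weeks or more, week 14 could catch it. A reader might infer that Aim 2 cannot be answered at all, but the documents do not support that. This is a worthwhile, low-cost improvement to a pilot.

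**What to change.** 1. In Sections 8.2.1.e, 8.5.2.b and 8.5.2.c and in Table 1, add the short-form Marijuana Withdrawal Checklist and the 12-item Marijuana Craving Questionnaire to the existing week 11, 12 and 13 visits.
2. In Section 8.9, state that withdrawal and craving scores will be reported by arm with confidence intervals for weeks 11 to 14 next to weeks 1 to 10, as descriptive estimates given about 9 per arm.
3. Present the weeks 11 to 14 scores alongside cannabis use over the same period (urine, diary and Timeline Follow Back), and make clear that Timeline Follow Back is collected at the week 11 to 13 visits.
4. If the forms are not added, limit Aim 2 conclusions to the on-drug period.

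The cost is a few extra minutes at three visits already scheduled and paid for, and one amendment to the schedule. No visit is added, and no dose or clinical rule is affected.
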